## 2. Introduction

Rheumatoid arthritis (RA) is a chronic systemic inflammatory disease that affects 0.8% to 1.0% of all populations. Rheumatoid arthritis primarily affects diarthrodial joints in a symmetrical distribution with an additive disease evolution over years (Scott et al 1987). The hallmark of the disease is damage and disruption of joint integrity, starting early in the course of RA. In most cases, bone erosions progress and lead to irreversible joint deformities. It is estimated that around one-third of patients have radiographic evidence of bone erosions at the time of diagnosis, and this increases to almost 60% 2 years after diagnosis (van der Heijde 1995). Unless the inflammatory processes are halted or controlled, the disease leads to substantial disability, comorbidities, and in some cases, premature death (Lard et al 2001).

CT-P10 is a monoclonal antibody, currently being developed by CELLTRION, Inc., which is intended to be formulated as a biosimilar candidate of Rituxan and MabThera, compounds with established efficacy in the treatment of active RA (MabThera 2015; Rituxan 2014). Rituximab is approved as Rituxan in the United States and as MabThera in other countries. CT-P10 can offer a more affordable treatment for RA than the originator protein if similar efficacy and safety are demonstrated and allow increased access to this valuable drug with a proven mechanism of action in RA patients. This is a similarity study that consists of 3 parallel arms: Rituxan (US-licensed), MabThera (EU-approved), and CT-P10. All statistical assessments will be direct comparisons between the treatment groups at specified time points.

This SAP covers all specified analysis and is based on the following documents:

- Protocol Version 5.1, including Country-Specific Protocol Amendment 1 (US) – 01 April 2016
- MSL Final Version 4.00 – 21 August 2015

According to the study protocol, the sponsor plans to prepare 2 Clinical Study Reports (CSRs). However, CSRs can be generated during the Study Period in addition to the 2 clinical study reports as planned for regulatory or academic purpose:

- To report data for each patient up to Week 24
- To report data after completion of study

This statistical analysis plan (SAP) defines the statistical methods and data presentations to be used by the CELLTRION biostatistics team for final analysis.

Note that the End-of-Study (EOS) visit only needs to be completed if the patient withdraws prior to study completion (Week 48 for Main Study Period, Extension Week 24 for Extension Study Period).

### 3. Objectives

Primary and secondary objectives are described below. Note that all patients from Part 1 of the study will be included in Part 2 of the study and undergo all assessments performed in Part 2. The decision to enter Part 2 of the study will not be influenced by the results from Part 1.

#### 3.1. Part 1

##### 3.1.1. Primary Objective

- To evaluate and compare pharmacokinetics in terms of area under the concentration-time curve from time 0 to the last measurable concentration over both doses of the first course ( $AUC_{0-last}$ ), area under the concentration-time curve from time 0 extrapolated to infinity over both doses of the first course ( $AUC_{0-\infty}$ ), and maximum serum concentration ( $C_{max}$ ) (after the second infusion) of CT-P10 to Rituxan, CT-P10 to MabThera, and Rituxan to MabThera during the first course of treatment (over the first 24 Weeks).

##### 3.1.2. Secondary Objective

- To assess the additional Pharmacokinetic (PK) variables of CT-P10, Rituxan, and MabThera, during the first course of treatment (over the first 24 Weeks)
- To evaluate the pharmacodynamics (PD) and safety of CT-P10, Rituxan, and MabThera (over the first 24 Weeks)

#### 3.2. Part 2

##### 3.2.1. Primary Objective

- To demonstrate that CT-P10 is similar to reference products (Rituxan and MabThera) in terms of efficacy as determined by clinical response according to change from baseline in disease activity measured by Disease Activity Score using 28 joint counts (DAS28) (C-reactive protein [CRP]) at Week 24.

##### 3.2.2. Secondary Objective

- To evaluate the additional PK (up to Week 48), efficacy, PD, overall safety, and biomarkers of CT-P10 compared with reference products

### 4. Investigational Plan

#### 4.1. Overall Study Design and Plan

This is a randomized, controlled, multicenter, 3-arm, parallel-group, double-blind, prospective, PK, efficacy, PD, and safety Phase 3 study. There will be up to 3 periods in this study:

[figure not shown]
- Screening Period: Week -6 through Week 0 (Day -42 to Day -1)
- Main Study Period: Week 0 through Week 48 (Day 0 to Day 336)
- Extension Study Period: Extension Week 0 through Week 24 (Extension Day 0 to Day 168)

The combined main and extension study duration will be up to 76 weeks after the Week 0 infusion. Extension Study Period will be initiated between Week 48 and Week 52 of the Entire Study Period. A schematic of the study design is presented in [Figure 1](#). There will be additional follow-up visits for patients with B-cell, IgM, and IgG values below the lower limit of normal

(LLN) or less than 50% of their baseline value until recovery is achieved for one of them. The term “Extension” will be used for all the visits in the Extension Study Period (i.e. Extension Week X or Extension Day X). Otherwise, visits will simply be stated as Week X.

**Figure 1: Study Schematic**

\* The third course of treatment will be initiated between Week 48 and Week 52 of the Entire Study Period based on the results assessed within 8 weeks from the Extension Week 0.

Any courses of treatment after the first course will be initiated if the following safety criteria are met:

- Absolute neutrophil count should be  $\geq 1.5 \times 10^3$  cells/ $\mu$ L (SI units:  $\geq 1.5 \times 10^9$  cells/L), platelet count should be  $\geq 75 \times 10^3$  cells/ $\mu$ L (SI units:  $\geq 75 \times 10^9$  cells/L), aspartate aminotransferase or alanine aminotransferase should be  $\leq 2.5$  times the upper limit of normal and levels of IgG should be  $\geq 500$  mg/dL (5.0 g/L), at the last blood sample analysis (i.e. Week 16 for second course of treatment and within 8 Weeks from the Extension Week 0 for third course of treatment).
- The patient has not developed any conditions which, in the investigators opinion, would preclude the patient receiving further courses of treatment (e.g., any new or uncontrolled disease such as, but not limited to, cardiovascular disease, or nervous system, pulmonary, renal, hepatic, endocrine, or gastrointestinal disorder).

[figure not shown]
Note that Part 1 and Part 2 of the study will follow the study schematic specified in [Figure 1](#).

In Part 1, the first approximately 189 patients with RA will be randomly assigned in a 1:1:1 ratio to 1 of 3 treatment groups, CT-P10, Rituxan, or MabThera (approximately 63 patients per treatment group).

In Part 2, approximately 172 subsequent patients with RA will be randomly assigned in a 1:1 ratio to 1 of 2 treatment groups, CT-P10 or Rituxan. In total, approximately 361 patients will be available for analysis.

Approximately 189 initial patients to be enrolled in the study will be assigned to Part 1 and all subsequent patients enrolled in the study will be assigned to Part 2. All patients from Part 1 of the study will be included in Part 2 of the study and undergo all assessments performed in Part 2. A schematic of study patient assignment for Part 1 and Part 2 is presented in [Figure 2](#). Part 2 will run independently and in parallel with Part 1.

**Figure 2: Schematic Diagram of Study Patients for the Main Study Period (up to Week 48)**

The Extension Study Period is designed to evaluate additional safety and immunogenicity.

Patients can continue to the Extension Study Period with an additional course of treatment regardless of the number of treatment courses they were treated with during the Main Study Period if the following conditions are met:

- Complete all of the scheduled visits up to Week 48 and
- Meet the predefined safety criteria.

The third course of treatment should be initiated between Week 48 and Week 52. If administration of the third course of treatment is deemed necessary to be initiated after Week 52 at the discretion of the investigator, the study infusion can be administered within 72 Weeks from the first infusion of the first course of treatment after discussion with the sponsor. In this case, the study infusion must be initiated no later than 52 Weeks from Day 0 for the last enrolled patient.

[figure not shown]
Note that patients, who have the End-of-Study (EOS) visit at Week 48, can participate in the Extension Study Period if the patients sign an informed consent form within 24 weeks from the EOS visit and do not have prohibited medications prior to entering the Extension Study Period.

All patients eligible for Extension Phase from the Rituxan group will be randomized again in a 1:1 ratio to the CT-P10 or Rituxan group at Extension Week 0. The randomization will be conducted and stratified by:

- The number of courses they are treated during the Main Study Period and
- The European League Against Rheumatism (EULAR)-CRP response status (responder vs. non-responder) assessed at Week 40.

To keep the blind during the study, stratification factors will be entered for all patients at Extension Week 0. In the case there were no EULAR-CRP response status available at Week 40, the last EULAR-CRP response status assessment done between Weeks 40 and 48 will be used. Baseline values for assessment of EULAR-CRP will be the last value from screening to Day 0 (Week 0) of the study. A schematic of the study patient assignment for this randomization is presented in [Figure 3](#).

**Figure 3: Study Schematic of Randomization**

Patients, who are assigned to receive CT-P10 with their first infusion in the study, will be considered as group 1 and maintain CT-P10 for the third course.

Patients, who are assigned to receive Rituxan with their first infusion in the study, will be randomized in a 1:1 ratio to group 2 (CT-P10 will be administered for the third course) and group 3 (Rituxan will be maintained for the third course) at Extension Week 0.

Patients, who are assigned to receive MabThera with their first infusion in the study, will be considered as group 4 and receive CT-P10 for the third course at Extension Week 0.

The third course of treatment will be initiated between Week 48 and Week 52 of the Entire Study Period if patients become eligible according to the predefined safety criteria for the course based on the results assessed within 8 weeks from the Extension Week 0. A visit window is not permitted on the day of second infusion for the third course of treatment.

Unscheduled visit(s) can be conducted for assessment of safety criteria until the initiation of the third course of treatment.

For patients who receive the third course of treatment at Week 48, the scheduled assessments and samplings should be performed according to the schedule of events and sampling schemes for the Extension Week 0. Otherwise, all scheduled assessments for Week 48 should be performed separately from the Extension Week 0 according to the schedule of events for Main Study Period.

All patients will receive MTX and folic acid concomitantly. Each patient may receive up to 3 courses of treatment; the first course will be an infusion of study drug (CT-P10, Rituxan, or MabThera) at Week 0 and Week 2. If patients meet the predefined safety criteria, patients are eligible to receive the additional course(s) of study drug (2 infusions in each course with a 2-week interval between infusions) at the discretion of the investigator.

For the second course of treatment in the Main Study Period, patients, who do not meet the predefined safety criteria, will not receive an additional course of treatment, but they will be followed according to the schedule of events for Main Study Period.

For the third course of treatment in the Extension Study Period, patients, who do not meet the predefined safety criteria within the time frame for the study drug infusion, will not receive an additional course of treatment and will be terminated from the study.

## 5. General Statistical Considerations

Continuous data will be summarized using descriptive statistics: n, mean, standard deviation (SD), median, minimum and maximum, unless otherwise indicated. Minimum and maximum will be presented to the same number of decimal places as the raw data, mean and median will be presented to one more decimal place than the raw data, and SD will be presented to two more decimal places than the raw data. If the geometric mean is to be presented, it will be set to the same precision as the mean. Percent coefficient of variation (CV) will be presented to one decimal place. P-values will be rounded to three decimal places. If a p-value is less than 0.001 it will be reported as “<0.001”. If a p-value is greater than 0.999 it will be reported as “>0.999”.

Categorical data will be summarized using counts and percentages. Percentages will be suppressed when the count is zero. A row denoted “Missing” will be included in count tabulations where necessary to account for missing values. The denominator for all percentages will be the number of patients within the treatment group for the all populations. Percentages will be presented to one decimal place.

Unless otherwise specified, summaries for visit-based data will only display scheduled visits.

Confidence intervals obtained from statistical procedures will be displayed to the same number of decimal places as the associated estimate.

All data will be displayed in listings. Unless otherwise specified, listings will be sorted by the treatment group, patient number, and assessment date or visit date, if applicable. In cases where more ordering is required, other variables will be included in the sort order as applicable.

### 5.1. Software

All analyses will be conducted using [REDACTED]. The [REDACTED] [REDACTED] will be used in order to derive summary scores for the SF-36 data prior to analysis. Pharmacokinetic parameters will be calculated with [REDACTED] [REDACTED]

### 5.2. Sample Size

For Part 1, 189 patients will be randomized in a 1:1:1 ratio to the CT-P10, Rituxan, and MabThera groups. Later, for Part 2, 172 patients will be allocated in a 1:1 ratio to the CT-P10 and Rituxan groups.

Part 1 of this study is powered to demonstrate PK similarity of CT-P10, Rituxan, and MabThera in  $AUC_{0-last}$ ,  $AUC_{0-\infty}$ , and  $C_{max}$ . Similarity will be demonstrated if the 90% confidence interval (CI) for the geometric mean ratio of CT-P10 to Rituxan and MabThera in  $AUC_{0-last}$ ,  $AUC_{0-\infty}$ , and  $C_{max}$  is within the bounds of 80% and 125%.

In Part 1, based on overall 90% power, Two one-sided alpha equal to 0.05, an interpatient CV in  $AUC_{0-last}$  of 30%, and a true of geometric mean equal to 1, fifty patients are needed in each treatment group being compared (50 patients in the CT-P10 treatment group, 50 patients in the MabThera treatment group, and 50 patients in the Rituxan treatment group: 150 patients total). The statistical power of each comparison, CT-P10 versus MabThera, CT-P10 versus Rituxan,

and MabThera versus Rituxan is 96.5% to achieve overall 90% power accounting for multiplicity with type II error correction. Allowing for a drop-out rate of 20%, 189 patients will be randomly assigned into the study in a 1:1:1 allocation.

In Part 2, the sample size of 322 evaluable patients (133 patients in the CT-P10 group and 189 patients in the reference products group [Rituxan and MabThera groups]) leads to approximately 90% power for the demonstration of similarity based on a two-sided 90% CI for the difference of mean change of DAS28 (CRP) score at Week 24 from baseline value between CT-P10 and reference products for an equivalence margin of  $\pm 0.50$ . In this sample size calculation, the common standard deviation of the mean change of DAS28 at Week 24 from baseline is assumed as 1.32 based on the CT-P10 1.1 study result for the therapeutic equivalence margin of  $\pm 0.50$ . Incorporating hypothesized drop-out rate of 10%, total sample size of 361 subjects (149 eligible patients in the CT-P10 and 212 eligible patients in the reference products group, including up to 63 patients from each of the CT-P10, Rituxan, and MabThera groups in Part 1) will be used in evaluation of efficacy endpoints.

In total, approximately 361 patients will be available for analysis (a total of approximately 149 patients for the CT-P10 group and 212 patients for the reference products group, including up to 63 patients from each treatment group in Part 1).

### **5.3. Randomization, Stratification, and Blinding**

Patients will be randomly assigned to a treatment group on Day 0 (before administration of study drug) by using a computer-generated randomization schedule prepared before the study. The randomization will be stratified by country, prior anti-TNF- $\alpha$  blocker status (inadequate response versus intolerant case), and Rheumatoid Factor (RF) or Anti-Cyclic Citrullinated Peptide (anti-CCP) status (both positive versus both negative versus either RF or anti-CCP negative). Patients with positive status for either RF or anti-CCP at screening will be classified as a positive.

This study will be double-blind. The blind should be broken only if specific emergency treatment would be dictated by knowing the study drug status of the patient. In such cases, the investigator must contact the medical monitor. If the investigator is unable to contact the medical monitor, the investigator may, in an emergency, determine the identity of the study drug by using the applicable procedure in the interactive web response system (IWRS) or interactive voice response system (IVRS).

The overall randomization code will be broken only for reporting purposes. The reporting of the co-primary endpoints for PK in Part 1 and Efficacy in Part 2 at Week 24 will be reported concurrently. The unblinded statistical analyses will be performed by CELLTRION. Only relevant [REDACTED] Biostatistics, Medical Writing and the sponsor will be unblinded at this stage; all other study personnel will remain blinded until the end of the study. Final determination of the analysis sets will occur prior to finalizing the database for each analysis. In addition, the blind will be broken for reporting to the Data Safety Monitoring Board (DSMB).

The randomization code will not be revealed to study patients, parents or guardians, study center staff, or investigators.

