5.5.1 Breaking the Blind

Under normal circumstances, the blind should not be broken. The blind should be broken only if specific emergency treatment would be dictated by knowing the study drug status of the patient. In such cases, the investigator must contact the medical monitor. If the investigator is unable to contact the medical monitor, the investigator may, in an emergency, determine the identity of the study drug by using the applicable procedure in the IWRS or IVRS (see study manual).

The date, time, and reason for the unblinding must be documented in the appropriate field of the eCRF. The medical monitor must be informed as soon as possible. Also, the unblinding process should be communicated with the medical monitor before unblinding.

Suspected unexpected SAEs, which are subject to expedited reporting, should be unblinded before submission to the regulatory authorities if required.

The overall randomization code will be broken only for reporting purposes. The reporting of the co-primary endpoints for PK in Part 1 and Efficacy in Part 2 at Week 24 will be reported concurrently. The unblinded analyses will be performed by **100**. Only relevant

and the sponsor will be unblinded at this stage; all other study personnel will remain blinded until the end of the study. Final determination of the analysis sets will occur prior to finalizing the database for each analysis. In addition, the blind will be broken for reporting to the DSMB.

The randomization code will not be revealed to study patients, parents or guardians, study center staff, or investigators.

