7.8.6 Interim Analyses

Although no formal interim analyses are planned, the sponsor plans to prepare 2 clinical study reports. However, clinical study report(s) can be generated during the Study Period in addition to 2 clinical study reports as planned for regulatory or academic purpose.

- 1. To report data for each patient up to Week 24
- 2. To report data after completion of study (including safety laboratory [B-cell, IgM and IgG] follow-up closed)

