10.2.2 Protocol Deviations

The investigator or designee must document and explain in the patient's source documentation any deviation from the approved protocol. The investigator may implement a deviation from, or a change of, the protocol to eliminate an immediate hazard to study patients without prior IRB/IEC approval. As soon as possible after such an occurrence, the implemented deviation or change, the reasons for it, and any proposed protocol amendments should be submitted to the IRB/IEC for review and approval, to the sponsor for agreement, and to the regulatory authorities, if required.

A deviation from the protocol is an unintended or unanticipated departure from the procedures or processes approved by the sponsor and the IRB/IEC and agreed to by the investigator. A significant deviation occurs when there is nonadherence to the protocol by the patient or investigator that results in a significant, additional risk to the patient. Significant deviations can include nonadherence to inclusion or exclusion criteria, enrollment of the patient without prior sponsor approval, or nonadherence to regulatory regulations or ICH GCP guidelines, and will lead to the patient being withdrawn from the study (Section 4.2).

Protocol deviations will be documented by the clinical monitor throughout the course of monitoring visits. Deviations from the protocol, including deviations of inclusion/exclusion criteria, will be assessed as "minor" or "major" in agreement with the sponsor. Deviations will be defined prior to unblinding. Principal investigators will be notified in writing by the monitor of deviations. The IRB/IEC should be notified of all protocol deviations in a timely manner.

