#### **5.6. Protocol Deviations**

Protocol deviation will be categorized as “major” or “other (or minor)”. Category of protocol deviation will be identified during the Data Review Meeting (DRM). A major protocol deviation is one that may affect the interpretation of study results or the patient’s rights, safety or welfare. Patients with major protocol deviation could be excluded only from the population (PD and/or Efficacy) that would be affected by the deviation.

Major protocol deviations are defined as follows:

- Mis-randomizations (defined as patients who received the another treatment to which they were assigned at any point during the study)
- Non-compliance of inclusion or exclusion criteria (to be identified by the [REDACTED] medical department via review of data sourced from the site monitoring database)
- Significant GCP non-compliance sites (to be identified by [REDACTED] as sites which have been closed due to suspected scientific misconduct and/or serious GCP non-compliance)
- Receipt of prohibited medication (based on agreement of each as from both [REDACTED] and CLT prior to database lock)

The major protocol deviations and other categories used for exclusion will be summarized for the all-randomized population by study part, treatment group. A listing of major protocol deviations for each patient will also be provided by treatment group.

The significant GCP non-compliance site will be excluded in all populations. The information of this site will be only listed in the Demographics and Treatment-emergent Serious Adverse Events listings, separately.

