## **11.1. ACR20, ACR50 and ACR70 criteria**

### **11.1.1. Proportion of ACR20, ACR50, and ACR70 Responders**

The American College of Rheumatology (ACR) criteria are a standard measure of clinical activity in rheumatoid arthritis patients. The ACR criteria used in this study are ACR20, ACR50, and ACR70.

A patient is defined as a responder according to ACR20 criteria if the following are fulfilled:

- A percentage decrease of at least 20% from baseline in the number of tender joints
- A percentage decrease of at least 20% from baseline in the number of swollen joints, and
- A percentage decrease of at least 20% from baseline in three of the following:
  - Patient's assessment of pain (VAS scale, mm)
  - Patient's global assessment of disease activity (VAS scale, mm)
  - Physician's global assessment of disease activity (VAS scale, mm)
  - HAQ estimate of physical ability
  - Serum CRP (mg/dL) concentration or ESR (mm/h)

Note: Percentage change = (Post-baseline value - baseline value)/baseline value \* 100

The following categories of patients are considered non-responders at each week respectively:

- Patients with an improvement according to the ACR criteria of less than 20%
- Patients who discontinue the study prior to the week of interest
- Patients with missing data for the evaluation of ACR20 criteria at the week of interest
- Patients with protocol prohibited initiation of new or increase in dose of RA medications that are deemed to affect efficacy. The ACR response status of these patients will be determined prior to database lock on an individual basis after agreement from the medical monitoring department of [REDACTED] and the sponsor.
- Patients requiring a surgical joint procedure prior to and including the week of interest. Surgical joint procedures will be defined as those patients with a reported joint surgery on the 'Joint Surgery Yes/No' eCRF page.

Any patient not satisfying any of the responder or non-responder criteria will be assigned a non-responder status. The ACR50 and ACR70 are calculated similarly to ACR20. However, a decrease of 50% and 70%, respectively, must be achieved.

The proportion of patients demonstrating ACR20, ACR50, and ACR70 (based on 1995 ACR criteria) will be summarized for the efficacy population, efficacy – 2nd treatment course in Main

Study Period subset and efficacy – Extension Study Period subset by treatment group at each visit, accordingly.

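### After the Week 24 code break the sponsor, by then unblinded, must still agree prohibited-medication deviations and the resulting ACR status for Week 48 and Extension Week 24

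*SAP*

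**What the plan says.** **Unblinding.** SAP 5.3 has the code broken for the concurrent report of the Part 1 PK endpoints and Week 24 efficacy. "The unblinded statistical analyses will be performed by CELLTRION", and "Biostatistics, Medical Writing and the sponsor will be unblinded at this stage", while everyone else working on the study stays blinded to its end. The sentence begins with a limit to relevant personnel, followed by a redaction. Protocol 5.5.1 gives the same rule: "and the sponsor will be unblinded at this stage; all other study personnel will remain blinded".

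**Reporting.** Protocol 7.8.6 plans two reports. The first is "To report data for each patient up to Week 24" and the second follows study completion. Week 48 and Extension results therefore belong to a later database lock.

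**Decisions that need the sponsor.** SAP 5.6 lists as a major deviation "Receipt of prohibited medication (based on agreement of each as from both" a redacted party and CLT, with that agreement timed to database lock. CLT is not in the abbreviation list; I read it as the sponsor. SAP 11.1.1 treats patients with prohibited new or increased RA medication as non-responders where the medication is judged to affect efficacy, and adds: "The ACR response status of these patients will be determined prior to database lock on an individual basis", after agreement between a redacted medical monitoring department and the sponsor.

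**A decision with no named decider.** SAP 11 drops affected visits from the efficacy analyses when such medication is judged to have influenced efficacy. It does not say who judges, or when.

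**The stated safeguard.** Protocol 10.2.2 has deviations graded minor or major in agreement with the sponsor and says: "Deviations will be defined prior to unblinding".

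**The concern.** Deciding whether a medication change counts against a patient is a judgement about outcome. It should be made without knowledge of treatment. Under the plan as written, one of the two parties who must agree may already hold the main-period code when the judgement concerns Week 48 or the Extension. A decision of this kind can turn a responder into a non-responder, remove a visit, or take a patient out of an efficacy or PD population. If those decisions track the treatment arm even slightly, the later ACR, DAS28 and related summaries are biased, in a direction nobody can determine afterwards. Documents that record no separation between code holders and deciders also leave the sponsor unable to show that it did not happen.

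**Working it through.** No power, margin or sample-size figure is in dispute. The check is one of timing and access.

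1. **Order of events.** The code is opened at the Week 24 report (SAP 5.3, Protocol 5.5.1). The second report comes after study completion (Protocol 7.8.6), so its lock falls after the sponsor has the code.

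2. **Which endpoints fall in the later cycle.** SAP 11 lists ACR20/50/70 at Week 24, Week 48 and Extension Week 24. The non-responder list in SAP 11.1.1 is applied week by week, so it governs the two later time points as well.

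3. **What the decisions are timed to.** SAP 5.6 and 11.1.1 time them to database lock. SAP 5.3 fixes analysis sets before the database is finalised for each analysis. In the Week 24 cycle, lock and first access to the code should coincide in order, so deciding before lock also means deciding blind. In the second cycle they separate: a decision can precede the final lock and still follow the code break.

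4. **Whether the protocol's safeguard closes the gap.** Protocol 10.2.2 covers deviations only; it does not mention ACR status or visit exclusion. If it means that categories are defined in advance, SAP 5.6 does that. Classifying an individual deviation that arises after the code break is different: the sponsor cannot agree it before an unblinding that has already happened.

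5. **Where the ACR discretion comes from.** Protocol 7.8.2.2 lists prohibited medication changes as non-response with no individual review. The case-by-case step appears only in SAP 11.1.1.

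6. **What the main-period code reveals.**
   - Week 48: all arms, so the CT-P10 versus reference comparison is fully exposed.
   - Extension: group 1 (CT-P10 throughout) and group 4 (MabThera to CT-P10) are identifiable, and patients of Rituxan origin are identifiable as a pool.
   - Group 2 versus group 3 is set by a second randomisation at Extension Week 0 (SAP 4.1). No text says that code is opened at the Week 24 report.

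7. **Size.** Using the planned numbers in SAP 5.2 (149 CT-P10, 212 reference), one reclassified patient changes a Week 48 ACR rate by 1/149 = 0.67 percentage points in the CT-P10 arm, or 1/212 = 0.47 points in the reference group. The documents do not say how many patients will have prohibited medication. If, purely as an assumption, between 1 and 5 CT-P10 patients were reclassified, the change would run from 0.67 to 5/149 = 3.4 points. These are sensitivities, not estimates of bias. The efficacy population and its second-course subset may be smaller than the randomised numbers, which would make the change per patient somewhat larger.

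**The case against.** The case against has real weight.

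- **The limit to relevant staff** may apply to the sponsor as well as to the contractor's functions, and a separate blinding plan may exist. That is possible. However, neither document names a sponsor sub-team or firewall, and SAP 5.6 and 11.1.1 simply require the agreement of CLT and of the sponsor.
- **The sponsor does not decide alone.** Both rules need a second party, and medical monitoring is not among the functions listed as unblinded. This stands and lessens the risk. It does not remove it, because the unblinded party can still withhold or give agreement.
- **Most major deviations are outside this discretion.** Of the four types in SAP 5.6, mis-randomisation is factual, and eligibility breaches and non-compliant sites are identified by redacted parties. Only prohibited medication needs agreement with CLT. This stands, although Protocol 10.2.2 brings the sponsor into minor/major grading generally.
- **Measurement is protected.** Patients, investigators and site staff stay blinded, so joint counts and VAS scores are not affected. This also stands.

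A reader might infer more than the text supports. Individual ACR review does not extend to all patients; it covers those with prohibited new or increased RA medication. SAP 11 does not assign visit exclusion to the sponsor; it assigns it to no one. Nor do the documents make Week 48 or Extension efficacy the basis of a similarity claim after switching. The similarity objective and the ±0.50 margin belong to DAS28 (CRP) at Week 24, and the Extension is described as serving additional safety and immunogenicity.

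**Conclusion.** The gap is real and narrow. As written, the plan lets unblinded sponsor staff take part in classifying outcomes for patients with prohibited RA medication at Week 48 and Extension Week 24, and it does not say who decides visit exclusions. The results affected are secondary and descriptive: the Week 48 comparisons and, in the Extension, groups 1 and 4 against the Rituxan-origin pool. The group 2 versus group 3 contrast is not exposed by the main-period code; it would be only if the second code were also opened early.

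It is tempting to read this as undermining the primary result. The documents do not support that: the Week 24 analysis is unaffected provided its data and analysis sets were fixed before the code break.

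The conclusion assumes that CLT is the sponsor and that no unseen blinding plan separates code holders from deciders. The effect is about 0.7 points per reclassified patient in the CT-P10 arm at Week 48, with the number of such patients unknown. This is worth correcting because the correction is cheap, not because a large bias has been shown.

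**What to change.** In SAP 5.6, 11 and 11.1.1, state that prohibited-medication deviations, visit exclusions and ACR status arising after Week 24 are decided only by staff with no access to either randomisation code: the contractor's medical monitoring staff, or named sponsor staff behind a documented firewall. Require each decision to be recorded before the final lock by people who are still blinded, so that the timing refers to code access as well as to lock. In SAP 5.3, say which sponsor staff are unblinded at Week 24 and when the Extension code is opened.

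For ACR status there is a simpler alternative: restore the automatic non-response rule of Protocol 7.8.2.2 and delete the case-by-case step. If that is chosen, the rule's mention of intra-articular corticosteroids must be reconciled with Protocol 5.7, which has its own provision for such injections after Week 24. Visit exclusions and deviations would still need a blinded decider.

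The cost is wording in the SAP and the blinding plan. No new data, visits or staff are needed.
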